7.5.1.7 Adverse Events and Device Deficiencies

Each subject will be monitored for:

- Serious adverse events
- Adverse device effects
- Device deficiencies (malfunctions, failures, or technical issues)

The investigator and sponsor will assess the incidence of adverse events comparatively between the treatment and control patients. If a significant difference is identified, further study implants will be paused until resolution is identified.

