5.4 Risk Mitigation Strategies

Stimulus interference with heart rhythm are mitigated in this protocol per study procedures sections 7.5.1.3.1 and 7.5.1.3.2 which describes cardiac rhythm monitoring. Pain due to stimulation is mitigated through device programming including programmable intensity and frequency settings and the optional burst mode as described in study procedures section 3.6.4.2. Percutaneous electrode exit site infection is mitigated by limiting TransAeris use to the hospital setting where proper exit site maintenance can be ensured. Infection is also mitigated by limiting the TransAeris stimulator to single patient use to prevent transmission of any bacterium from patient to patient on the device.

Additionally, procedure-related risks were mitigated through a prior feasibility study (IDE's G150040 & G170294) which investigated the safety and performance of the TransLoc electrodes including their insertion and removal and investigated the safety and performance of the TransAeris stimulation on open cardiac surgery patients. In total, 176 electrodes were successfully placed in 44 patients during these two pilot studies. Electrodes were placed concomitant to a primary surgical procedure done using one of three approaches: laparoscopic, open abdominal, and open chest. Electrode stability was demonstrated by the collection of daily diaphragm EMG readings. No unretrieved device fragments were left with the removal of electrodes. No device or procedure related adverse events from implantation through electrode removal were reported.

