7.5.1.3.1 Treatment (Tx) Group

TransAeris use begins, in the Tx group as soon as practical. TransAeris stimulation will not begin unless the patient is connected to cardiac monitoring. The cardiac rhythm will be observed for any potential cardiac capture when stimulation is initiated, or any changes are made. The observation of cardiac rhythm interaction is recorded with the stimulator settings on the daily post-op case report form, page 5. TransAeris stimulator settings (stimulus intensity, stimulus frequency, and burst on/off) will be programmed to optimize diaphragm recruitment without compromising patient comfort. Refer to section 3.6.4.2 Device Programming. If stimulation settings cannot be adjusted or the stimulation cannot be applied without eliciting patient discomfort or pain due to the stimulation, then an adverse event indicated on the daily post-op case report form and an adverse event case report form, page 11, should be completed. Stimulation pain should be assessed daily using verbal and/or non-verbal cues from the patient using the visual analog scale shown below. In the event of pain that cannot be eliminated by reducing stimulation intensity then it should be recorded as such on the adverse event case report form.

TransAeris stimulation will continue as needed until the patient is successfully weaned. Stimulation may continue beyond successful weaning at the clinician's discretion to provide any additional support to avoid reintubation, but no longer than 30-days post-op.

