7.5.1.3.2 Standard of Care (SOC) Group

The SOC group does not receive TransAeris stimulation for the first 120 hours of mechanical ventilation. SOC group patients will not be stimulated unless they are still on mechanical ventilation at 120 hours, at which point they will have an EMG recording made on the case report form, page 6. If intact bilateral EMG is not observed a competing event will be recorded on the competing event case report form, page 10. Otherwise the patient will be identified as a Cross-over patient on the daily post-op case report form, page 5, and follow the process for the Tx group as identified in section 7.5.1.3.1, with the start of TransAeris stimulation.

Any device deficiencies or competing events, that would inhibit or preclude weaning, should be indicated on the daily post-op case report form and the associated detail case report form for device deficiencies, page 12, or competing events, page 10, should be completed for all patients, Tx, SOC or cross-over.

A final EMG recording will be performed prior to electrode removal in all patients. Recordings will be made for a period of at least one minute during quiet, resting breathing or quiet, mechanical ventilation support.

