15. ADVERSE EVENTS, ADVERSE DEVICE EFFECTS AND DEVICE DEFICIENCIES

15.1 Definitions as per ISO 14155:2020 & MDR 2017/745

Adverse Event (AE): Any untoward medical occurrence, unintended disease or injury or any untoward clinical signs, including an abnormal laboratory findings, in subjects, users or other persons, in the context of a clinical investigation, whether or not related to the investigational medical device.

Note 1: This definition includes events related to the investigational medical device or the comparator.

Note 2: This definition includes events related to the procedures involved.

Note 3: For users or other persons, this definition is restricted to events related to the use of investigational medical devices or comparators.

Adverse Device Effect (ADE): Adverse event related to the use of an investigational medical device.

Note 1: This definition includes adverse events resulting from insufficient or inadequate instructions for use, deployment, implantation, installation, or operation, or any malfunction of the investigational medical device.

Note 2: This definition includes any event resulting from use error or from intentional misuse of the investigational medical device.

Note 3: This includes 'comparator' if the comparator is a medical device.

Serious Adverse Event (SAE): Any adverse event that led to any of the following:

a) Death,

b) serious deterioration in the health of the subject, that resulted in any of the following:

1) a life-threatening illness or injury,

2) a permanent impairment of a body structure or a body function,

3) hospitalization or prolongation of patient hospitalisation

4) medical or surgical intervention to prevent life-threatening illness or injury, or permanent impairment to a body structure or a body function,

5) chronic disease,

c) foetal distress, foetal death or a congenital physical or mental impairment or birth defect

Note 1: Planned hospitalization for a pre-existing condition, or a procedure required by the CIP, without serious deterioration in health, is not considered a serious adverse event.

Events that do not meet these criteria are considered non-serious.

Serious Adverse Device Effect (SADE): Adverse device effect that has resulted in any of the consequences characteristic of a serious adverse event.

Unanticipated Serious Adverse Device Effect (USADE): Serious adverse effect which by its nature, incidence, severity or outcome has not been identified in the current risk assessment.

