15.3.1 Investigator reporting Responsibilities

Investigators must report to the sponsor, without delay (immediately) and not later than 3 calendar days after his awareness, all adverse device effects (ADEs), device deficiencies and serious adverse events (SAEs) study subjects experience during participation in this investigation.

Each reported event must be appropriately documented to include the event's serious criterion, relatedness, treatment, and resolution. All reported events that remain unresolved should be re-assessed until the event resolves or the subject's study participation is complete. In the event of subject death, the investigator will make reasonable effort to obtain a death summary, autopsy report, etc.

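### The between-arm adverse event comparison in 7.5.1.7 is not like with like for non-serious background events, because these are generally captured only if the open-label site attributes them to the device

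*Combined protocol and SAP*

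**What the plan says.** Section 7.5.1.7 names three classes to be monitored in each subject: serious adverse events, adverse device effects and device deficiencies. It then turns to a broader term: "The investigator and sponsor will assess the incidence of adverse events comparatively between the treatment and control patients". The consequence follows directly: "If a significant difference is identified, further study implants will be paused until resolution is identified". The section does not define a significant difference.

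The investigator's duty in 15.3.1 covers the same three classes: "all adverse device effects (ADEs), device deficiencies and serious adverse events (SAEs) study subjects experience during participation in this investigation". Tables 2a-2d in 7.5.1 add competing events but no general adverse event line. Section 15.1 defines an adverse device effect by its link to the device: "Adverse event related to the use of an investigational medical device".

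On surveillance, 7.5.1.3.1 (treatment group) says: "The cardiac rhythm will be observed for any potential cardiac capture when stimulation is initiated, or any changes are made". The result goes on the daily form: "The observation of cardiac rhythm interaction is recorded with the stimulator settings on the daily post-op case report form, page 5". The same section asks for a daily assessment of stimulation pain. For controls, 7.5.1.3.2 says: "The SOC group does not receive TransAeris stimulation for the first 120 hours of mechanical ventilation". Controls still ventilated at 120 hours then follow the treatment-group process. The study is open label, and all subjects receive electrodes (7.1).

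**The concern.** Randomization supplies an unstimulated group that could show how much non-serious rhythm disturbance and pain follows a sternotomy without stimulation. That background rate is useful only if the same events are recorded in both arms by the same rule. Here the rule for a non-serious event runs through attribution to the device, decided by staff who know the arm, and the stimulation checks apply only to stimulated patients.

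The error can go either way. An ordinary postoperative rhythm change put down to stimulation counts in the treatment arm, while the same change in a control has no stimulation to be put down to. Conversely, a real increase that the site judges unrelated may be recorded in neither arm. The comparison can pause implants, identifying safety concerns is a stated objective (6.2), and the data are to inform a pivotal trial (8.1).

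**Working it through.** **Step 1. Which events enter the comparison, by arm, in the first 120 hours.** This follows from 7.5.1 (Tables 2a-2d), 7.5.1.3.1, 7.5.1.3.2, 7.5.1.7, 15.1 and 15.3.1.

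| Event | Treatment | Control | Like with like? |
|---|---|---|---|
| Serious adverse event, any cause | collected | collected | yes |
| Electrode-related device effect | can be recorded | can be recorded (electrodes in all subjects) | yes |
| True stimulation effect | can be recorded | cannot occur | a real device effect, not bias |
| Non-serious background rhythm change or pain | generally only if attributed to the device | same rule, but cannot be attributed to stimulation | no |

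The problem lies in the last row.

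**Step 2. Passages that point to wider recording.**
- 7.5.1.3: the procedure form notes the occurrence of an adverse event.
- 7.5.1.4: events that impede weaning are recorded in both groups, even if unrelated to the device.
- 7.5.1.5: subjects are monitored for adverse events, without qualification, after electrode removal.
- 7.5.1.6: the follow-up 30 days after removal asks about any post-procedure complications.
- 15.2: causality is to be assessed for all adverse events.

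None of these creates a general, cause-neutral record of non-serious events during the stimulation period. The 15.2 wording presupposes one that Tables 2a-2d, 7.5.1.7 and 15.3.1 do not provide. The passages must be reconciled.

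**Step 3. Illustration of size.** The plan gives no figure for this comparison, so there is nothing to reproduce.

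Inputs from the documents: 30 implanted subjects, half per arm, so 15 v 15 (synopsis and 7.4.2); two-sided p below 0.05 for any p-value reported (8.3).

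Assumptions: Fisher's exact test stands in for the undefined significant difference; the true event rate r is the same in both arms; the fraction of events captured is c_T in treatment and c_C in control.

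Recorded counts are Binomial(15, r × c_T) and Binomial(15, r × c_C). The chance of a significant treatment excess is the sum of the joint probabilities over all tables with p < 0.05 and more events in treatment. At 15 v 15, 4 v 0 gives p = 0.100 and 5 v 0 gives p = 0.042. With one control event, 7 v 1 is the smallest significant excess.

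| r | c_T / c_C | Expected recorded, treatment v control | Chance of a significant treatment excess |
|---|---|---|---|
| 30% | 100% / 100% | 15 × 0.30 = 4.5 v 4.5 | 0.8% |
| 30% | 100% / 50% | 4.5 v 2.25 | 7.8% |
| 30% | 80% / 10% | 3.6 v 0.45 | 19.2% |
| 30% | 100% / 20% | 4.5 v 0.9 | 24.4% |
| 20% | 100% / 20% | 3.0 v 0.6 | 9.5% |
| 10% | 100% / 20% | 1.5 v 0.3 | 0.9% |

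In every unequal-capture row the expected recorded counts differ although the true rates are equal. Whether that would trigger a pause depends on the assumed values. With equal capture in both arms (100% or 50%; true rates 10% to 50%), the chance of a significant treatment excess is at most about 0.9%.

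**The case against.** The strongest reply has five parts.

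1. **The checks are specific to stimulation.** They look for cardiac capture, rhythm interaction and stimulation pain, none of which exists without stimulation, so a treatment-only excess in them is a finding about the device. This stands. Only background events that are misattributed, or missed, distort the comparison. It also follows that asking unstimulated controls about stimulus interaction with a pacemaker or defibrillator would add little.

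2. **Other sections record more widely, and the case report forms are not in the documents.** This stands in part. One cannot say flatly that a control's event is never recorded; one can say that the sections conflict and that no section requires it.

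3. **The independent Medical Monitor (section 16) reviews seriousness and relatedness of reported device effects.** This limits misattribution to the device. It does not retrieve non-serious events judged unrelated and never reported.

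4. **The arithmetic rests on assumed values.** This stands. The pilot saw 0 of 10 for heart rhythm interference, implanted-device interaction and stimulation pain (5.2). If 30% of stimulated patients had such an event recorded, 0 of 10 would have probability 0.7^10 = 2.8%; at 20%, 0.8^10 = 10.7%. The upper rows of the illustration therefore sit uneasily with the pilot. Sections 8.3 and 8.4.3 plan no hypothesis tests, so the Fisher trigger is also an assumption.

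5. **The stakes are limited.** Serious events are collected in both arms, the primary safety endpoint (8.4.1) is the incidence of serious adverse device effects, and the action is a pause in a descriptive 30-patient study. This stands, and it keeps the point at the level of a recommended improvement.

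A reader might also infer that 5.4 miscites its sources: "Stimulus interference with heart rhythm are mitigated in this protocol per study procedures sections 7.5.1.3.1 and 7.5.1.3.2 which describes cardiac rhythm monitoring". The documents do not support that. Section 7.5.1.3.2 brings in the treatment-group process when a control is first stimulated, so both citations are apt. Nor should one infer daily rhythm checks under stimulation: 7.5.1.3.1 ties the observation to the start of stimulation and to setting changes, and only stimulation pain is assessed daily.

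**Conclusion.** The point holds for non-serious background events in the ICU, chiefly ordinary rhythm change and pain. For these, the comparison in 7.5.1.7 mixes occurrence with attribution in an open-label trial, and the stimulation checks reach controls only after cross-over. It can show a false treatment excess or miss a real one, and it feeds a pause whose criterion is undefined.

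It would go too far to call the whole comparison biased by construction. Serious events enter whatever their cause, electrode-related effects can arise in both arms, and effects truly due to stimulation are properly seen only in stimulated patients.

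The size cannot be derived from the documents. The illustrative 8% to 24% at a 30% background rate, falling to about 1% at a 10% rate, depends wholly on the assumed rates, capture fractions and test.

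**What to change.** - **Daily post-op form (page 5), already completed for every patient on each day in protocol (7.5.1.3).** Add entries for new rhythm disturbance, pain, exit-site infection requiring antibiotics and bleeding after electrode removal. Complete them in both arms on the same days, whatever the presumed cause.
- **Section 7.5.1.7.** State that the between-arm comparison uses all serious adverse events regardless of relatedness, plus these events collected alike. Report adverse device effects by arm descriptively, with the Medical Monitor's review, as device effects and not as a randomized comparison.
- **Reconciliation.** Align the references to adverse events in 7.5.1.3, 7.5.1.4, 7.5.1.5, 7.5.1.6 and 15.2 with Tables 2a-2d, 7.5.1.7 and 15.3.1, so that the site knows which events to record.
- **Minimum alternative.** If the form is not changed, restrict the comparison in 7.5.1.7 to serious adverse events and other events collected alike in both arms.

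The cost is a few entries on an existing form, a paragraph of text and a little extra transcription. Raw event counts will look higher in both arms, because unrelated background events will now be listed.

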7.5.2 Equipment Used for Study Evaluations

The diaphragm EMG will be recorded with an EMG recorder suitable for recording continuous EMG, such as the Crystal PSG device from Cleveland Medical Devices or other similar device.

7.5.3 Description of Activities Performed by Sponsor Representatives

Synapse Biomedical, Inc. will provide onsite training, technical support, and troubleshooting assistance as needed, including support for TransLoc electrode implantation and device programming and use in the patient room.

7.6 Monitoring Plan

The sponsor, Synapse Biomedical, will monitor the study in accordance with its standard operating procedures to ensure that the study is conducted, recorded, and reported in accordance with the investigational plan, investigator agreement, and applicable EC and regulatory requirements.

Prior to the initiation of the study, the monitor will assess the study site via virtual meeting or physical meeting to assure that the investigator has adequate resources to conduct the clinical study and that the investigator understands his or her obligation regarding: conducting the study in accordance with the agreement with the sponsor, the investigational plan, the EC requirements, and French regulations; obtaining EC review and approval of the clinical study and ensure continuing review; obtaining informed consent; maintaining study records; permitting inspection by French regulators; submitting reports; protocol deviations; investigational device accountability; and financial disclosure, if applicable.

During a monitoring visit, the monitor will review: the continued adequacy of resources to conduct the clinical study; EC approval and other study-related EC records; informed consent records; investigational device storage facilities and accountability practices; investigational device accountability records; correspondence (with the EC, sponsor, or CA, if applicable) including required reports; protocol deviation records; and subject case report forms, adverse device effect reports, and their consistency with source documents.

7.7 Data Protection

All participant data collected during the course of this investigation will be kept strictly confidential. Any information that could identify a subject will remain with the investigator where it will be archived with study documents. Data from all participants will remain pseudo-anonymized for the purposes of data analysis. Data collected for the purposes of this study should be made available for the sponsor/designee at all monitoring visits.

Should the investigation require future review, it may be necessary to allow limited access to the sponsor/designee and regulatory authorities for audit purposes only. They will be granted direct access to the study subjects' original medical records for verification of clinical study procedures and/or data, without violating the confidentiality of the subjects to the extent permitted by the law and regulations.

The sites and the sponsor must follow the General Data Protection Regulation (GDPR) 2016/679, as it applies to the protection and privacy of subject data.

In any presentations of the results of this study or in publications, the subjects' identity will remain confidential.

Study participants and related data will be identified by a unique study identification number. This will not include the participant's contact or identifying information.

The clinical investigation will be registered in a publicly accessible database, on www.clinicaltrials.gov, in accordance with the FDA Modernization Act prior to enrollment of the first subject. Results of the clinical investigation will be made public on this website in accordance with the applicable requirements.

8. STATISTICAL CONSIDERATIONS

8.1 Study Design and Statistical Objective

This study is designed to gather data on the use of TransAeris in subjects identified prior to surgery to be at greater risk of prolonged mechanical ventilation after surgery. Data collected will be compared qualitatively to the relevant clinical literature and used to inform the design and statistical parameters for a subsequent multi-center pivotal trial.

8.2 General Considerations

Continuous data will be summarized using descriptive statistics: mean, standard deviation, median and interquartile range. Categorical variables will be summarized using frequency counts and percentages. For events which can occur more than once in a single subject (e.g., adverse events), the primary analysis will be based on the count of subjects experiencing the event; both patient and event counts will be reported.

All statistical analyses will be performed in STATA version 13.1 or later, or other widely accepted statistical analysis software packages.

8.3 Analysis Population and Significance Testing

The primary analysis will consist of all available data from all enrolled subjects, referred to in ICH E9 ("Statistical Principles for Clinical Trials") as the full analysis set. As the intended analyses of study outcomes

are descriptive in nature, *a priori* hypothesis tests are not proposed; however, any p-values computed and reported will be two-sided, with values less than 0.05 indicating statistical significance.

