8.4.2 Primary Efficacy Endpoint

The primary efficacy endpoints are the mechanical ventilation time and proportion of patients successfully weaned at 48- and 120-hours post-op. These will each be evaluated separately for efficacy. A wean will be considered successful if the patient is not reintubated within 48 hours of extubation. The mechanical ventilation time will be the cumulative proportion of time on mechanical ventilation over the 48- or 120-hour period from the entry to the ICU (recorded as ICU Admit Time on the procedure information case report form). If an extubation is attempted but is not successful (i.e., less than 48 hours) then that time will not be considered off of mechanical ventilation. The proportion weaned will be derived from the cumulative incidence function (CIF) of a competing risk analysis.

Data will be analyzed for all patients and using a predictive enrichment threshold of patients on mechanical ventilation. The enrichment strategy is applied to identify patients that may more likely respond to TransAeris stimulation and decrease variability, as per FDA guidance.(14) As the TransAeris treatment is not intended to produce immediate results, but rather is intended to prevent or treat VIDD, patients that are on MV for short periods are expected to have improved spontaneously and thus increase the variability in the outcome measures if included in analysis. Similarly, patients, during the initial hours of mechanical ventilation with paralytic anesthesia still impacting contraction, are not expected to respond to the treatment and thus excluding patients that are weaned from mechanical ventilation during the initial 10 hours post-op will be considered as not part of the predictive enrichment analysis. The data will be considered non-proportional and will be assessed using non-parametric techniques.

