8.4.3 Secondary Endpoints

Secondary endpoints are defined as follows:

- All-cause mortality through 30 days
- Mechanical Ventilation time, as the cumulative time on mechanical ventilation from ICU entry and paralytic reversal to successful wean,
- Ventilator-free days, defined(15) as time free from mechanical ventilation during first 28 days, where:
$$\begin{aligned} VFD28 &= (28 - \text{Time on MV}) \text{ if Time on MV is less than 28 days;} \\ &= 0 \text{ if Time on MV} \geq 28 \text{ days} \\ &= 0 \text{ if death within 28 days} \end{aligned}$$
- Hospital length of stay (admission to discharge)
- ICU length of stay
- Change in median frequency and total power of the power density spectrum (PSD) analysis of inspirations at baseline, pre-stimulation, and post-stimulation in cross-over control patients

All endpoints will be summarized and reported descriptively to characterize outcomes. No *a priori* hypothesis testing is planned for this study.

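### Section 8.3 disclaims hypothesis tests but labels any p-value below 0.05 statistically significant, across four unranked primary efficacy measures in a 30-patient pilot with no confidence intervals planned

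*Combined protocol and SAP*

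**What the plan says.** On testing, section 8.3 calls the analyses descriptive and says that a priori "hypothesis tests are not proposed". The same sentence then adds that "any p-values computed and reported will be two-sided, with values less than 0.05 indicating statistical significance". Section 8.4.3 repeats that no a priori "hypothesis testing is planned for this study", and section 8.5 says the same, resting the 30 subjects on precision of estimation.

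On endpoints, section 8.4.2 states: "The primary efficacy endpoints are the mechanical ventilation time and proportion of patients successfully weaned at 48- and 120-hours post-op". Ventilation time is the "cumulative proportion of time on mechanical ventilation over the 48- or 120-hour period", so there are four measures. Of these it says: "These will each be evaluated separately for efficacy".

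On populations, section 8.4.2 states: "Data will be analyzed for all patients and using a predictive enrichment threshold of patients on mechanical ventilation". The enriched set leaves out patients weaned in the first 10 hours. Section 8.3 does name a primary population: "The primary analysis will consist of all available data from all enrolled subjects". Section 8.4.2 does not repeat that ranking.

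Section 8.2 lists means, standard deviations, medians, interquartile ranges, counts and percentages. No section specifies a confidence interval for a difference between groups, a multiplicity adjustment, or a statement that p-values are nominal.

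**The concern.** The two halves of the sentence in 8.3 pull against each other. A plan that tests nothing has no use for a significance threshold, but this one supplies a threshold and applies it to any p-value that is reported. Four separately evaluated measures in two populations give eight primary efficacy comparisons to which the label could be attached.

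The primary objective (section 6.2) is to judge whether the expected benefit is credible, and section 8.1 says the data will inform the design and statistical parameters of the pivotal trial. Two things are at stake. A chance finding could be reported as significant. And at this size, a difference large enough to earn the label would, under the sponsor's own assumption, be much larger than the truth. If it were carried into the pivotal sample size, that trial would be too small. A confidence interval would show the uncertainty directly, and none is planned.

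**Working it through.** **Inputs from the documents.** Section 4.2: of patients with prolonged ventilation, 65.9% of controls and 45.9% of treated patients on ventilation at 48 hours; positive predictive value 56.5%, so 43.5% weaned before 24 hours; 34.8% of patients with prolonged ventilation still ventilated at 120 hours. Synopsis and section 8.5: 30 patients, half per arm, so 15 v 15.

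**The plan's own figure.** Section 4.2 gives about 192 patients for the pivotal study. Power is not stated; I assume 80%, with two-sided 5% and pooled variance. With a mean rate of 0.559:

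n per arm = [1.96 × √(2 × 0.559 × 0.441) + 0.842 × √(0.659 × 0.341 + 0.459 × 0.541)]² / 0.20² = 95.6, so 96 per arm and 192 in total.

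192 / 0.565 = 339.8, the plan's 340. The figures reproduce, so these rates are a fair basis for what follows.

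**False positives under no effect.** I simulated null trials of 15 v 15, at least 4,000 per setting. Wean times were interpolated between the section 4.2 rates. The documents do not give the share weaned before 10 hours, so it was varied from about 20% to 70% of those weaned before 24 hours. Section 8.4.2 says only that non-parametric techniques will be used, so proportions were compared by Fisher's exact test (low end) and by uncorrected chi-square (high end), and ventilation time by the Wilcoxon rank-sum test. Competing events were not modelled.

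| Comparisons | Chance of at least one p<0.05 |
|---|---|
| Four measures, all patients | about 7% to 11% |
| All eight (both populations) | about 10% to 16% |

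**Effect implied at 48 hours in all patients.** These rates are derived and are not printed in the plan:
- Control: 0.565 × 65.9% = 37.2%
- Treatment: 0.565 × 45.9% = 25.9%
- Difference: 11.3 points

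**Precision with 15 per arm.** SE = √(0.372 × 0.628/15 + 0.259 × 0.741/15) = 0.168. The 95% half-width is 1.96 × 0.168 = 0.33, or ±33 points.

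**Power and exaggeration if 11.3 points is true.** From enumeration of all binomial outcomes, 15 v 15:

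| Test | Power | Smallest difference reaching p<0.05 | Mean absolute difference given p<0.05 | Ratio of that mean to 11.3 |
|---|---|---|---|---|
| Chi-square | 10.7% | 26.7 points | 39.9 points | 3.5 |
| Fisher | 4.1% | 33.3 points | 46.1 points | 4.1 |

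The normal approximation gives power of 9.6%. Even the smallest difference that earns the label is 26.7/11.3 = 2.4 times the implied effect by chi-square, or 33.3/11.3 = 2.9 times by Fisher.

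**The case against.** The best defence is that nothing on the efficacy side turns on a p-value. The clause is conditional: it governs p-values only if some are computed. Section 8.1 describes a qualitative comparison with the literature, 8.4.3 a descriptive report, and 8.6 rules out early stopping for success. Section 4.2 itself expects a 40-patient study to be statistically inconclusive. Section 8.3 already names all enrolled subjects as the primary analysis and 8.7 repeats it, so the two populations are ranked and the enriched set is arguably supportive. All of this stands, and it limits the point to how results will be labelled.

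It does not remove the point. The four measures remain unranked even within the all-patient analysis. Section 8.4.2 puts both populations under the primary endpoint without repeating the ranking. And if p-values are reported, the clause prescribes the label.

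The simulation can also be questioned. The early-wean share is an assumption, competing events are left out, and simple proportions stand in for the cumulative incidence function that 8.4.2 specifies. The ranges are therefore approximate.

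**Conclusion.** The point holds as an interpretation flaw in a descriptive pilot. With no true effect, the chance of at least one p<0.05 is about 7% to 11% in the primary population and 10% to 16% over all eight comparisons, against a nominal 5%. Exaggeration is the larger problem: at the effect implied by section 4.2, power is about 4% to 11%, and results with p<0.05 overstate that effect about 3.5- to 4-fold on average. These figures rest on 15 per arm, the derived 37.2% v 25.9%, and the simulation assumptions stated above.

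Three stronger readings are tempting but not supported:
- A reader might compute 1 − 0.95^8 = 34% as the false-positive risk. That needs eight independent comparisons, whereas the populations are nested, the 48- and 120-hour windows overlap, and both kinds of measure come from the same ventilation record.
- A reader might infer that any p<0.05 here must be a large overestimate. That follows only if the true effect is near 11.3 points, which is an assumption.
- A reader might infer that the plan sets up an efficacy test and fails to control its error. The documents propose no test and tie no efficacy decision to a p-value.

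**What to change.** In section 8.3, end the p-value sentence after the statement that p-values are two-sided, deleting the 0.05 clause. Add that any p-values are nominal and will not be described as significant.

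In section 8.4.2, report each primary efficacy difference between groups with a two-sided 95% confidence interval. State that the all-patient analysis named in 8.3 is primary and the enriched-set analysis supportive.

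One place to check at the same time: section 7.5.1.7 pauses implants on a significant difference in adverse events without defining the word. The edit to 8.3 should not leave that term hanging on a deleted clause.

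The cost is a few sentences. Sample size, data collection and patient care are unchanged. The sponsor gives up the option of calling a result significant, and the published intervals will be wide, about ±33 points at 48 hours.
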